The findings summarized above have been the rationale for the use of psychosocial interventions in the rehabilitation of cancer. Recent meta-analysis findings suggest that psychosocial treatment can be effective in improving quality of life parameters after primary cancer treatment (Fors et al., 2010). Furthermore, psychosocial support treatment decreased disease recurrence and increased life expectancy in a cohort of cancer survivors (n=227, 11-year followup) (Andersen et al., 2008). In a study involving both PCa and breast cancer patients, a mindfulness based program enhanced quality of life and decreased stress symptoms, altered cortisol and immune patterns consistent with less stress and mood disturbance (Carlson et al., 2007). In addition, it was also shown in a randomized clinical trial that chronic inflammation, negative mood, and fatigue were alleviated by a yoga based program in breast cancer survivors (Kiecolt-Glaser et al., 2014). Similarly, another randomized trial showed that a yoga program improved quality of life and physiological effects associated with radiotherapy in breast cancer survivors (Chandwani et al., 2014).

Prostate cancer (PCa) is the most prevalent cancer in men (Desantis et al., 2014). PCa has the highest Medicare expenditure than any other cancer that affects older men. Modern tailored

treatment regimens have resulted in longer life expectancy, but also longer treatment periods, which lead to treatment related morbidity, as well as adverse side effects, including psychological distress and pain (e.g. Penson and Chan, 2007; Bhoojani et al., 2008)). For example, depression has serious implications for outcomes and recovery from PCa as reflected in debilitating effects on health related quality of life, functional status, health resource utilization and cost (Bhoojani et al., 2008; Pirl et al., 2008; Reeve et al., 2009, Weber et al., 2008). Consistently, a recent National Cancer Institute based evaluation recommended four patient-reported outcomes to be routinely incorporated into clinical trials: pain, fatigue, mental well-being, and physical well-being (Chen et al., 2014).

As indicated in some of the examples above, many patients with cancer turn to integrative medicine (IM) modalities to help manage their symptoms (for a review, see Dobos et al., 2013). In addition to best standard of care from western perspective, IM encompasses a broad array of heterogeneous treatments, ranging from herbal medicine to yoga. Yoga has recently undergone empirical investigation, as exemplified above, as a potentially beneficial intervention for patients with cancer. An ancient Eastern tradition estimated to be a 5000-year-old discipline originating from India (Udapa and Singh, 1972), a yoga program encompasses various domains, including ethical disciplines (e.g. non-harm in actions and words), physical postures (asanas), and spiritual practices, with the goal of uniting the mind, body, and spirit for health and self-awareness. Hatha-yoga, the classical form of yoga, is considered to improve bodily functions through the manipulation of cardiovascular, respiratory, metabolic, and other control mechanisms. Whereas asanas are generally familiar, the pranayama, the breathing practices, and the central role that they have in yoga, are not usually sufficiently emphasized.

One of the most widely used breathing techniques derived from yoga is Sudarshan Kriya (SK) (Murthy et al, 1998; Janakiramaiah et al., 2000) that is used in conjunction with other central aspects of yoga. SK is traditionally understood to use specific rhythms of the breath to eliminate stress, support the various organs and systems within the body, transform overpowering emotions and restore peace of mind. Recent medical research on SK and related practices (SK&P), also referred to as SK yoga or SKY, has indicated significant effects on various aspects of the physiology and the psychology of the participants.

For example, studies demonstrated that SKY has important antidepressant effects in clinical settings (Murthy et al, 1998; Janakiramaiah et al., 2000) and is comparable to the antidepressant drug Imipramine in its efficacy. Effect of SKY on psychological health is not limited to clinical patients. **[name]** and co-workers conducted a controlled study and found that participants in the SKY group, but not the control group, significantly lowered their degree of anxiety, depression and stress, and also increased their degree of optimism (Kjellgren et al., 2007).

Another study found significantly lower levels of blood lactate in practitioners of SKY compared with the control group. Conversely, the levels of superoxide dismutase (SOD), catalase, and glutathione, three major defenses against oxidative stress, were all found to be significantly higher in SKY practitioners compared with the control group (Sharma et al., 2003). These data suggest that people who practice SKY have an improved antioxidant status and defense against oxidative stress.

Various additional studies indicate that SKY results in improved physical and psychological health. For example, there are interesting findings on the effects of SKY on brain function, indicative of a state of wakeful alertness (Bhatia et al., 2003). In addition, there appears to be strengthening of the immune system, as measured by increases in natural killer (NK) cell number, in both healthy people, but also in cancer patients (Kochupillai et al., 2005). Furthermore, SKY has been shown to be effective in post-traumatic stress disorder (Carter et al., 2013) and in a randomized trial **[name]** and co-workers found that it affected the circulating immune cells at the level of gene expression (Qu et al., 2013).

The goal of this proposal is to systematically study the possible impact of SKY on PCa patients. The studies will include not only psychological assessment through self-report questionnaires on pain, fatigue and psychological well-being, but also objective measures on basic physiological parameters, including the stress hormone cortisol and cytokine IL-6. **Our hypothesis** is that there would be a measurable effect of SKY on psychological distress in PCa patients on the

parameters to be tested, and that this will correlate with favorable changes in physiological parameters that may impact disease progression.

Our preliminary data from two clinical trials we conducted in students (Kjellgren et al, 2007) and healthy volunteers (Qu et al, 2013) support our hypothesis (see above, studies by [name] and co-workers, as referenced in Kjellgren and Qu papers). There was decreased anxiety, depression and stress in one study, and improved physiologic changes in the other. These preliminary results give us confidence that the proposed study will show the hypothesized improvements in the health status and physiological parameters of patients with PCa.

Specific Aims:

This study will have two parts:

1. Determine any change in pain, fatigue and psychological well-being as a result of SKY in PCa patients.
2. Assess changes in some physiological parameters in response to SKY in the same subjects, compare these with those from Part 1, and assess whether these translate into clinical effects.

Subjects:

PCa patients that have been treated with radiotherapy will be recruited to the study (Winship Cancer Institute Clinic, contact person [name]).

Inclusion criteria: Age \geq 45 years; having finished radiotherapy at least two months ago; ability to speak/read English and give informed consent; having an interest in being part of a study to evaluate yoga-derived exercises and eager to practice some kind of relaxation exercise daily for 3 months.

Exclusion criteria: Having a diagnosis of psychiatric illness or other major illness in addition to PCa, such as other cancers, uncontrolled hypertension, lung disease, liver disease or heart disease.

Approval by the IRB Committee will be applied for. All participants will sign consent forms and throughout the study they will be treated according to the ethical guidelines, in addition to standard treatment for PCa. Participants will be informed that the data obtained in this study will be kept in a separate approved password controlled secure database at the Winship Cancer Institute of Emory University, and that the data from this database will be linked to the approved clinical database in the same institution. They will also be told that they participate by their free will and that they are free to leave the study whenever they wish without giving any reason for it and not risking any consequence for the standard treatment that they will receive.

The men will be randomly assigned to one of two groups:

1. No treatment control.
2. Healing Breath Program (SKY).

SKY includes gentle stretches (yoga postures), specific breathing exercises (see below), and cognitive coping and stressor evaluation strategies. SKY is traditionally understood to dissolve emotional distress and create the subjective experience of rest and well-being. The instructors in SKY are trained by the International Art of Living Foundation. The yoga intervention is held over 13 weeks: in Week 1, subjects will receive yoga instruction for approximately 3 hours daily on 5 consecutive weekdays, and in Weeks 2-13, subjects will attend yoga instruction once a week for about 2 hours.

The breathing techniques that are part of SKY are: (a) Three-Stage Pranayama with Ujjayi or "Victory Breath", (b) three sets of Bhastrika or "Bellow's Breath", and (c) SK, and they are practiced in that order. The breathing practices are done in a sitting posture, either in a chair or on the floor. Eyes are kept closed throughout the sessions.

A total of 50 patients will be randomized into the two study arms. 20 subjects are aimed at in each group, but to account for drop-out/exclusion, 25 subjects will be recruited per group (to accommodate drop-out/exclusion rate of 20%). Both groups will be tested at the time of recruitment

to the study as Pretest 1. The SKY intervention will be given in groups of 10-15 patients and the tests will be performed again within 2 weeks of the first week of yoga (Posttest 1). The control group will be tested at the same time. Posttest 2 will be performed within 2 weeks of completing the 13-week yoga program, using the same parameters. **In addition to daily home practice, there will be weekly follow-up sessions for the SKY group** which will last about 2 hours during which exercises will be performed in a group and questions that may arise related to the practice will be answered. Control subjects will be offered 1-week of yoga classes after the end of the study (ie, after post-test-2)

Below is a brief flowchart of the study timeline:

Week --	Recruitment (3 months prior to the start of yoga)
Week --	Pretest 1 (within 2 months prior to starting yoga)
Week 1-13	SKY intervention (13 weeks)
Week 2-3	Posttest 1 (within 2 weeks of the first week of yoga)
Week 14-15	Posttest 2 (within 2 weeks of the last week of yoga)

Research design and methods:

Aim 1. Determine any change in pain, fatigue and psychological well-being as a result of SKY in PCa patients.

We will assess psychological wellness parameters in the PCa subjects at the time points as described above. This will be done by administering standardized questionnaires which are enumerated below:

1. The Hospital Anxiety and Depression Scale (HADS): A 14-item self-rating scale, measuring anxiety and depression (Zigmond and Snaith, 1983).
2. The EORTC Quality-of-life Questionnaire (EORTC QLQ-C30). A cancer-specific 30-item questionnaire (Aaronson et al., 1993) incorporating 5-functioning scales, a global health-status/QOL scale and symptoms assessment. In addition Functional Assessment of Cancer Therapy-Prostate (FACT-P) questionnaire will be utilized.
3. The Life Orientation Test – Revised (LOT-R): A 10-item self-report scale, measuring expectations about positive outcome in general (Scheier et al., 1994)
4. 36-item short-form health survey (SF-36) vitality scale, a reliable and valid measure of energy/fatigue in the past month (Stein et al., 1998).
5. Pain will be assessed with the BPI-SF questionnaire (Cleeland and Ryan, 1994).

Aim 2. Assess changes in some physiological parameters in response to SKY.

In addition to the self-report measures described above, it is important to use objective measures to determine if SKY practice results in physiological effects. As reviewed above, previous studies on SKY have indicated various physiological effects, such as positive influence on the immune system, support of the antioxidants system, and effects of gene expression in the circulating immune cells. To evaluate if similar effects are observed in PCa patients, and whether these correlate with the measures in Part 1, venous blood, saliva, and hair will be collected at the three time points and the following tests will be performed:

1. Enzymes indicative of antioxidant status, i.e. Superoxide Dismutase (SOD) and Glutathione peroxidase (GPX) (based on previous studies by Sharma et al., 2003). We will also measure serum 8-isoprostane level, an indicator of oxidative stress.
2. Inflammatory markers, i.e. Interleukin 1 and 6, Tumor Necrosis Factor alpha (TNF α), and C-reactive protein (since these cytokines are important in carcinogenesis and may be modulated by psychosocial intervention therapies).
3. Saliva cortisol taken between 07 and 09 am, as measure of psychophysiological stress (Levine et al., 2007).

4. Hair cortisol, using a 1-inch strand of hair taken from the back of the head, as a measure of psychophysiological stress.
In addition, two epigenetic tests will be performed:
5. RNA will be isolated from the peripheral blood mononuclear cells (PBMCs) and gene expression changes will be assessed as previously done in response to the SKY regimen (Qu et al., 2013).
6. DNA will be isolated from the PBMCs and potential DNA methylation changes in response to SKY regimen.

The levels of these endpoints (1-3) and gene expression profiles will be compared during the different time points as described above.

STUDY FLOW CHART:

Yoga group:

1. **Prestudy evaluations:** Questionnaires, and blood/saliva/hair samples (within 2 months prior to starting Yoga instructions)(Pre-test 1)
2. **Yoga instructions**
Week 1 – Yoga instruction (3 hours daily for 5 days)
Week 2-13 –Yoga instruction (2 hours on one day each week)
3. **Post-study evaluations (1):** Questionnaires, and blood/saliva/hair samples (within 2 weeks of the first week of yoga)(Post-test 1) (Week 2-3)
4. **Post-study evaluations (2):** Questionnaires, and blood/saliva/hair samples (within 2 weeks of the last week of yoga)(Post-test 2) (Week 14-15)

Control group:

- 1) Prestudy evaluations: Questionnaires, and blood/saliva/hair samples (after consenting) (Pre-test 1)
- 2) Post-study evaluations (1): Questionnaires, and blood/saliva/hair samples (within 6-8 weeks from the pre-test 1 evaluations)(Post-test 1)
- 3) Post-study evaluations (2): Questionnaires, and blood/saliva/hair samples (within 2-4 months after Post-test 1 evaluations)(Post-test 2)
- 4) Control subjects will be offered 1-week of yoga classes after the end of the study (ie, after post-test-2)

Statistical Considerations:

Fifty subjects should be a sufficient sample size because in our previous study with a sample size of 14 subjects we were able to observe statistically significant changes (Qu et al, 2013). Comparisons will be made with the Student's t test. A value of $P < 0.05$ will indicate statistical significance.

Research team:

The main coordinator of the project is [name], Department of Hematology and Medical Oncology, Emory University. The collaborator partners are: [name], Department of Psychiatry; [name], and [name] from Department of Radiation Oncology, Emory University.

Yoga instructions will be provided by Art of Living Center instructors in Atlanta. They have agreed to provide the SKY intervention proposed in this study.

Epigenetic, biochemical and inflammatory marker laboratory tests will be done at [name] Laboratory. [name] has conducted research using similar methodology (testing of wellness parameters, cancer related endpoints, and gene expression) (Kjellgren et al., 2007; Qu et al., 2013) which will facilitate the current work.

Ethical considerations: All work will be done in accordance with the ethical principles of human subject use and the rules of the Institutional Review Board (IRB) at Emory University. All

members of the research team have participated in similar studies before involving human subjects and are thus familiar with all the procedures that are necessary.

REFERENCES

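### The promised link between psychological and physiological change has no analysis that can test it, and any correlation added to fill the gap must account for arm

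*Combined protocol and SAP*

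**What the plan says.** The combined protocol and SAP promises an association in three places.

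- The hypothesis in the introduction, after predicting an effect on psychological distress, adds that "this will correlate with favorable changes in physiological parameters that may impact disease progression".
- Specific Aims, item 2, will measure physiological change, then "compare these with those from Part 1, and assess whether these translate into clinical effects".
- Research design and methods, Aim 2, asks "whether these correlate with the measures in Part 1".

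Statistical Considerations is the only place that names a method: "Comparisons will be made with the Student's t test", and a P value below 0.05 "will indicate statistical significance". The end of Aim 2 adds that the levels of endpoints 1 to 3 and "gene expression profiles will be compared during the different time points as described above". That describes comparisons over time, not an association with the questionnaires.

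No correlation, regression or mediation method is named. No pair of variables, change interval or handling of arm is given for the association. On size, "A total of 50 patients will be randomized into the two study arms" and "20 subjects are aimed at in each group".

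**The concern.** A t test handles one variable at a time and asks whether two means differ. It makes no use of the fact that a symptom change and a biomarker change belong to the same man. The association in the hypothesis is a statement about exactly that pairing. If the plan is followed as written, this half of the hypothesis is either left untested or read off two separate arm differences, which do not establish it.

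Adding a correlation without further detail leaves the main choice open. The comparator is no treatment, and the sponsor expects SKY to improve both domains. If that is right, the arms separate on both axes. A correlation over all men then picks up the arm difference even when, within each arm, symptom change and biomarker change are unrelated. With no rule in the plan, that choice and the choice of pairs would be made after the data are seen.

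**Working it through.** **The plan's own figure.** With 20 evaluable men per group and 20% drop-out or exclusion: 20 / (1 − 0.20) = 25 per group, 50 in total. This agrees with the plan. The target of 20 cannot itself be re-derived, because no effect size, SD or power is given.

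**What a t test can show.** Rearranging the biomarker changes among the men within each arm leaves every arm mean and SD, and so every between-arm t test, unchanged. The within-arm correlation with symptom change can take very different values under such rearrangement. The t tests therefore carry no information about that link.

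**What pooling would do.** Let d1 and d2 be the arm differences in the two changes, in within-arm SD units. With equal arms and no within-arm association, the expected pooled correlation is

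r = (d1·d2/4) / √[(1 + d1²/4)(1 + d2²/4)].

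For d1 = d2 = 0.8: 0.16 / 1.16 = 0.14. For d1 = d2 = 1.0: 0.25 / 1.25 = 0.20.

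The documents give no effect sizes, so a range is assumed, equal for both measures. The rates come from 50,000 simulated trials per row (bivariate normal changes, 5% level). The plan does not state sidedness; two-sided is assumed.

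| Effect on both (SD) | Expected pooled r | Pooled test, 20 per arm | Arm-adjusted test, 20 per arm | Pooled test, 25 per arm |
|---|---|---|---|---|
| 0.3 | 0.02 | 5.2% | 5.0% | 5.3% |
| 0.5 | 0.06 | 6.5% | 5.2% | 7.0% |
| 0.8 | 0.14 | 13.7% | 5.1% | 15.9% |
| 0.91 | 0.17 | 18.9% | 5.1% | 22.6% |
| 1.0 | 0.20 | 24.3% | 4.9% | 29.3% |

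The 0.91 row is the effect for which a t test with 20 per arm has 80% power. If only one measure responds (0.8 or 0.9 SD on one, 0 on the other), the pooled test rejects 4.9% of the time at 20 per arm, so there is no inflation.

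Hand check at 0.8 SD, using Fisher's z: atanh(0.138) × √37 = 0.84. The rejection probability is Φ(0.84 − 1.96) + Φ(−0.84 − 1.96) ≈ 0.135, in line with the simulation.

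**What 40 men can detect.** Fisher's z for a partial correlation with k covariates has standard error 1/√(N − 3 − k).

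- Arm only (k = 1): tanh[(1.960 + 0.842)/√36] = 0.44.
- Arm and two Pretest 1 values (k = 3): tanh[(1.960 + 0.842)/√34] = 0.45.
- The same with alpha halved to 0.025: tanh[(2.241 + 0.842)/√34] = 0.48.
- SKY arm alone (n = 20, no covariates): 0.59.

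With adjustment for arm only, a true r of 0.3 would be detected with power of about 46%.

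**The case against.** The strongest reply is that the gap is one of specification only. Questionnaires and samples come from the same men at the same three evaluations, so the data for an association analysis will exist. That stands. A reader might infer that the trial cannot answer its mechanistic question at all; the documents do not support this.

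A second reply is that no pooled correlation appears anywhere in the plan. That also stands. The rates above describe a hazard to avoid when the gap is filled, not an analysis the sponsor proposed. A reader might further infer that pooling would find a false link whenever SKY affects both domains. The figures do not bear this out: even at 1.0 SD on both measures, about 76% of pooled tests would not be significant, and at 0.3 to 0.5 SD the inflation is slight.

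A reader might also multiply six questionnaires by nine markers to get 54 pairs, and expect 54 × 0.05 = 2.7 chance findings per post-test. The plan nowhere says that every pair will be tested, and the sum assumes that all are null. It is not part of this point.

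Two limits of the remedy are fair. A common arm-adjusted correlation mixes natural covariation in untreated men with covariation under SKY, so it does not by itself show that changes caused by SKY are linked. And choosing HADS leaves pain and fatigue, also in Aim 1, outside the main association test. HADS matches the psychological distress named in the hypothesis, but the choice belongs to the sponsor.

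**Conclusion.** The concern holds in this form: an association is promised in the hypothesis, in Aim 2 and in the methods, and the one stated method cannot test it. That conclusion rests on the text alone and needs no assumption.

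The requirement to account for arm is a condition on the remedy. Its size depends on assumed effects: from about 5% false positives at 0.3 SD to about 24% at 1.0 SD on both measures, with 20 per arm and no within-arm association, and no inflation if only one measure responds. The arm-adjusted test keeps about 5% throughout.

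The between-arm comparisons are not affected. The gap should be closed, but it does not invalidate the trial.

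**What to change.** Add to Statistical Considerations:

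- The association is estimated as a partial correlation, with confidence interval, between the Pretest 1 to Posttest 2 change in HADS and the change over the same interval in cortisol and in IL-6, adjusted for arm and Pretest 1 values. The introduction says only cortisol, while Aim 2 lists both saliva and hair, so the sponsor must name one in advance.
- Alpha is split over the two pairs, or both are labelled exploratory. All other pairs are exploratory.
- With 40 evaluable men, 80% power is reached only for |r| of about 0.45, or about 0.48 with alpha split.

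In Specific Aims, item 2, limit the clinical effects to the Part 1 scales, because no disease-progression outcome is among the listed assessments.

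The cost is a few sentences and one more analysis of data already to be collected. The downside is that the stated detectable correlation is visibly large.

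### The plan foresees exclusions after randomisation on unstated grounds and specifies only a t test, so a completers-only comparison could result

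*Combined protocol and SAP*

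**What the plan says.** The Subjects section sets out two arms, no treatment and SKY: "The men will be randomly assigned to one of two groups". On numbers it says "A total of 50 patients will be randomized into the two study arms", and next that "20 subjects are aimed at in each group, but to account for drop-out/exclusion, 25 subjects will be recruited per group". The reason given for the larger number is "to accommodate drop-out/exclusion rate of 20" per cent. Drop-out and exclusion are merged into that single rate. No grounds for excluding a man once he is in the trial appear anywhere; the only exclusion criteria listed are the eligibility criteria in the same section. Men are also told that "they are free to leave the study whenever they wish without giving any reason for it".

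Statistical Considerations has three elements. It says fifty subjects should be enough, because a previous study of 14 found significant changes. On the analysis it says "Comparisons will be made with the Student's t test". It then gives the threshold: P below 0.05 "will indicate statistical significance". It does not name an analysis population, say whether the t test is between arms or over time, mention the Pretest 1 values, or say how missing outcomes are handled. The Study Flow Chart schedules two post-tests in each arm but does not say what happens to a man who stops yoga before them.

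**The concern.** Randomisation makes the two arms comparable only while the men compared are the men randomised. Here the allowance is taken from men already randomised, and part of it is labelled exclusion, which is a decision by the study team in a trial where allocation is known. A t test with no further instruction simply omits anyone without an outcome. With a target of 20 remaining men per arm, a comparison of those who finished is the easy default.

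The arms also give different reasons to leave. SKY asks for daily classes in week 1, weekly classes in weeks 2 to 13, and home practice. The control arm has no programme to abandon. All Aim 1 outcomes (HADS, QLQ-C30, FACT-P, LOT-R, SF-36 vitality, BPI-SF) are self-reports by men who know their arm. If men who find SKY burdensome or unhelpful are the ones missing, those left would look better than the arm as randomised. A treatment effect could then be reported that partly reflects who stayed.

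**Working it through.** **1. The plan's own figure.** Target 20 per arm, loss 20% (Subjects): 20 / (1 - 0.20) = 25 per arm, and 2 x 25 = 50. This reproduces exactly. Because 50 is also the number randomised, the 10 men allowed for (50 - 40) are lost after randomisation. The target of 20 cannot itself be derived, since no effect size, SD or power is given.

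**2. Burden by arm.** SKY classes (Subjects; Study Flow Chart): 5 days x 3 h + 12 weeks x 2 h = 15 + 24 = 39 h, plus daily home practice. Control: none before Post-test 2.

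**3. Bias if a completers-only t test were used.** Assumptions, none from the documents: no true effect; 20% of SKY men are lost and would have scored delta SD worse than those who stay; control losses are random; SD 1 among those analysed; two-sided test (sidedness is not stated). The full-arm mean is then 0.2 x delta below the mean of those who stay, so bias = 0.2 x delta.

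With 20 per arm, SE = sqrt(2/20) = 0.316, df = 38, critical t = 2.024, and the noncentrality is bias / SE.

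| delta | Bias (SD) | Noncentrality | Rejection under the null |
|---|---|---|---|
| 0.5 | 0.10 | 0.316 | 6.1% |
| 1.0 | 0.20 | 0.632 | 9.5% |

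**4. Check by simulation.** 40,000 replicates, no true effect, 5 of 25 SKY men removed, with removal correlated to poor outcome; control losses none or random.

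| Correlation | Bias (SD) | Rejection |
|---|---|---|
| 0 | 0 | 5% |
| 0.3 | 0.10 | 6% |
| 0.5 | 0.17 | 8-9% |
| 0.7 | 0.23 | 12-13% |
| 1.0 | 0.33 | 23-24% |

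**5. Same loss mechanism in both arms.** In the same simulation the bias is about zero at every correlation (-0.001 to -0.003 SD). Rejection is 5.1% to 6.7% for correlations up to 0.7, and 10.1% in the extreme case where the five worst scorers in each arm are always the ones lost. So the bias depends on losses differing between arms, not on loss alone.

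**6. Precision.** SE ratio for 25 against 20 per arm: sqrt(20/25) = 0.894, about 11% narrower. The difference detectable with 80% power by a two-sided 5% t test falls from 0.91 to 0.81 SD. Both gains need all 25 outcomes per arm to be observed.

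**The case against.** The strongest reply is that a recruitment allowance is ordinary planning and says nothing about who is analysed. That is right. A reader might infer that the plan lays down a completers-only t test on self-selected men. The documents do not support this: no sentence limits the t test to completers, and Statistical Considerations speaks of fifty subjects, not 40. Self-selected would in any case describe men who choose to leave, not men removed by the team, and the plan does not separate the two.

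A reader might also infer that men can be excluded for poor attendance, or that those who stop yoga are refused the post-tests. Neither is stated. Exclusion could mean men later found ineligible, and the yoga-arm tests are scheduled without an attendance condition. The statement about freedom to leave is a consent right, not an analysis rule.

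Nor is the direction of bias settled. Every man must be eager for daily relaxation practice to be eligible, so men allocated to no treatment may leave out of disappointment. Step 5 shows that equal mechanisms give about zero bias, and at delta 0.5 the inflation in step 3 is small.

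All of this limits how strongly the point can be put. It does not supply what is missing: grounds for exclusion, an analysis population, and rules for missing data and for men who stop yoga.

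**Conclusion.** The point holds as a gap in protection of the randomised comparison. The plan foresees exclusion after randomisation without saying why a man would be excluded, and its only analysis instruction is a t test that ignores baseline and drops men without outcomes. A completers-only comparison could follow; it is not prescribed. Bias toward SKY is likely, given the one-sided burden and unblinded self-report, but not certain.

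The size rests on assumed inputs. For losses in SKY only, delta of 0.5 to 1.0 gives 0.10 to 0.20 SD and a true error rate of 6.1% to 9.5% in place of 5%. Loss completely determined by outcome takes this to 0.33 SD and 23-24%. The change is worth making because it is cheap and leaves the sample size alone. Confidence is moderate, since the likely pattern of losses cannot be read from the documents.

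**What to change.** **In Subjects**, state that the 20% allowance is for missing outcome data, and that no man is excluded from the analysis after randomisation for non-attendance or for stopping yoga. If a man is later found ineligible, any removal must rest on information from before randomisation and be judged without knowledge of his arm or outcome.

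**In Statistical Considerations**, state that:

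- all randomised men are analysed in their assigned arm;
- Post-test 1 and Post-test 2 are sought regardless of yoga attendance, unless the man withdraws consent;
- the main between-arm comparison is adjusted for the Pretest 1 value, by ANCOVA or by a mixed model using all available Post-test 1 and 2 data;
- a sensitivity analysis covers missingness that depends on the unobserved outcome, which neither model removes by itself;
- a completers-only t test is supportive only.

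**Cost.** Wording, a modest amount of extra analysis, and a few more questionnaires from men who stop classes, at visits already planned. The estimated effect may be smaller because non-attenders are kept. The gain in precision of about 11% should not be promised, since it applies only if all 25 outcomes in each arm are obtained.
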